3.2 Exclusion Criteria

3.2.1 Evidence of metastatic disease on imaging studies (CT, x-ray, and/or bone scan).

3.2.2 Diagnosis of diabetes mellitus defined as:

- Fasting blood glucose > 126 mg/dl or,
- Random blood glucose > 200 mg/dl
- Hemoglobin A1C $> 6.5\%$

- 3.2.3** Need for treatment with any conventional modality for prostate cancer (surgery, radiation therapy, and hormonal therapy).
- 3.2.4** Treatment with any investigational drug 30 days prior to randomization.
- 3.2.5** Radiation therapy within prior 6 months (prophylactic radiotherapy to prevent gynecomastia within 4 weeks prior to randomization is allowed).
- 3.2.6** Known hypersensitivity to metformin.
- 3.2.7** Prior history of lactic acidosis.
- 3.2.8** Any history of myocardial infarction in the past 12 months.
- 3.2.9** Subjects who consume more than 3 alcoholic beverages per day.
- 3.2.10** Subjects with serious intercurrent illness, including, but not limited to, ongoing or active infection, symptomatic congestive heart failure, unstable angina pectoris, cardiac arrhythmia, or other nonmalignant medical or psychiatric illness that is uncontrolled or whose control may be jeopardized by the complications of this therapy or may limit compliance with the study requirements (at the discretion of the investigator).
- 3.2.11** Patient with previous or concurrent malignancy. Exceptions are made for patients who meet any of the following conditions: Basal cell or squamous cell carcinoma of the skin or prior malignancy that has been adequately treated and patient has been continuously disease free for ≥ 2 years.
- 3.2.12** Subjects currently treated with metformin and/or bicalutamide or who have been treated with metformin and/or bicalutamide in the past 6 months.
- 3.2.13** Subjects who have taken 5 α -reductase inhibitors (finasteride or dutasteride), saw palmetto, or PC-SPES within the last 6 weeks are ineligible. Subjects will be eligible for the study after the wash out period of 6 weeks.

4.0 PROTOCOL MANAGEMENT

4.1 Registration and Randomization Procedures

Participants may be registered from 8:00 am to 4:00 pm EST excluding holidays by emailing the Investigator-Sponsored Research Unit (ISRU) at: [contact]. Eligible participants will be entered on study centrally once the following items have been received by email:

- Completed registration form
- Consent and HIPAA signature pages
- Eligibility checklist

Following registration, participants must begin protocol treatment within 7 calendar days of registration. Issues that would cause treatment delays must be discussed with the Sponsor-Investigator. If a registered participant does not receive protocol therapy following registration, the participant will be recorded as withdrawn from study. The Study Monitor must be notified as soon as possible if a participant does not begin protocol treatment as scheduled. For additional registration questions, please email [contact] or call [contact].

The FCCC ISRU will notify the site by email once registration is confirmed and the sequence number has been assigned. Participants must be registered and have received a sequence number prior to the initiation of treatment.

Exceptions to the current registration policies will not be permitted.

5.0 TREATMENT PLAN

5.1 Informed Consent and Consent for Tissue Collection

Prior to study entry, all patients must sign informed consent. All patients will be presented with the option to donate a biopsy specimen for research purposes, and consent for this will be documented separately within the informed consent.

5.2 Baseline Disease Assessment

Imaging will be performed as described in the Study Calendar (Section 6.0).

5.3 Study Treatment

Upon initiation of treatment, both agents will be administered orally at the assigned doses and schedules. One cycle = 28 days = 4 weeks. Treatment will be administered on an outpatient basis.

5.3.1 Treatment ARM A

Cycles 1 – 2: Observation without treatment

Cycles 3 – 8: Bicalutamide 50 mg daily, orally, continuously to the end of study (week 32).

5.3.2 Treatment ARM B

Cycles 1 - 2: In order to minimize gastrointestinal discomfort, metformin dosing will be ramped up over a period of 2 weeks. Metformin treatment will

be started at 500 mg BID (Dose Level -2) and increased by an increment of 500 mg daily every week +/- 2 days provided no grade 2 or higher gastrointestinal toxicity is noted. If grade 2 or greater gastrointestinal toxicity occurs during the first 4 weeks of treatment, the subject will be evaluated every 2 weeks until resolution of toxicity to grade 0 or 1 and, then, the metformin dose will be increased to the next dose level. The target dose of metformin is 1000 mg BID. If patient cannot tolerate higher dose, metformin will continued at maximum tolerated dose as listed below.

Dose level	Metformin dose
Dose Level -2 (Week 1 +/- 2 days)	500 mg twice daily
Dose Level -1 (Week 2 +/- 2 days)	500 mg breakfast / 1000 mg at bedtime
Dose Level 0 (Week 3 and later)	1000 mg twice daily

Cycles 3 – 8: Continue metformin at maximum tolerated dose (up to 1000 mg BID). Start bicalutamide 50 mg/daily, orally, on a continuous basis to the end of study (week 32).

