5.5.1. Dose Modifications for Metformin

The major toxic effects of metformin which limit dose are gastrointestinal (nausea, abdominal bloating, diarrhea). During the ramp-up period, subjects experiencing gastrointestinal symptoms should be encouraged to take tablets with food. If no improvement, subjects should try taking study medication every other day for two weeks, once per day for two weeks and then twice per day thereafter. Subjects not tolerating study medication after this approach may go off study treatment but Investigators are urged to re-challenge willing subjects 4 weeks later. Dose adjustments, for reasons of toxicity, will be as in the tables below. (Please note that none of the recommended dose adjustments require splitting of study medication pills. Pills are not to be split or crushed, prior to taking, for any reason.) Breaks of up to 4 weeks consecutively or 8 weeks overall are allowed to ascertain the cause of the adverse events.

Gastrointestinal Toxicity Toxicity / Adverse Event	Grade	Investigator Action
Gastrointestinal Toxicity of any type	Grade 1	Patient should be encouraged to remain on full dose. If patient is unwilling, stop study treatment for one week. For subjects who were unwilling to remain on full dose, after one week without study drug, follow the ramp-up procedure. If Grade 1 symptoms persist or recur during the ramp-up or at full dose and the patient is unwilling to continue, follow instructions for Grade 2 toxicity.
Nausea Distension/Bloating Diarrhea Gastrointestinal - Other	Grade 2 (or higher)	Reduce to 500 mg BID for one week. If symptoms resolve or are Grade 1 only, after one week, resume full dose (1000 mg BID). If symptoms persist or recur at Grade 2 or higher, stop study treatment for 4 weeks, then resume study treatment as follows: Re-start study drug according to original ramp-up schedule. If toxicity persists or recurs, the study drug should be adjusted to the maximum dose that is tolerated with Grade 1 toxicity or lower. A second attempt to increase to full dose should be made 4 weeks later and if the full dose is not tolerated at that time, the maximum tolerated dose should be used for the remainder of the study.

15-1015

Hepatic dysfunction* (bilirubin > ULN except for Gilbert's Disease)	Grade 1 (or greater)	Hold study drug for up to 4 weeks. If bilirubin returns to normal within that time frame, begin 500 mg BID for 4 weeks, then 1000 mg BID.

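### Grade 2 or higher gastrointestinal toxicity in the first weeks of metformin has conflicting instructions with no stated precedence; lead-in exposure for the same event can be equal or differ up to about threefold.

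*Combined protocol and SAP*

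**What the plan says.** Four places in the protocol bear on the same event.

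- **Section 5.3.2 and the Schema (same wording).** Metformin starts at 500 mg BID and is "increased by an increment of 500 mg daily every week +/- 2 days provided no grade 2 or higher gastrointestinal toxicity is noted". The scheduled levels are 1000 mg/day in week 1 (Dose Level -2), 1500 mg/day in week 2 (Dose Level -1) and 2000 mg/day from week 3 (Dose Level 0). On toxicity of grade 2 or greater in the first 4 weeks: "the subject will be evaluated every 2 weeks until resolution of toxicity to grade 0 or 1 and, then, the metformin dose will be increased" by one level. No reduction or interruption is stated.
- **Section 5.5.1, opening text.** This covers gastrointestinal symptoms of any grade during the ramp-up. Tablets are first taken with food. If that fails, "subjects should try taking study medication every other day for two weeks, once per day for two weeks and then twice per day thereafter". The dose per intake is not given, and the first two steps do not appear among the dose levels in 5.3.2.
- **Section 5.5.1, table, row for grade 2 or higher.** "Reduce to 500 mg BID for one week", then 1000 mg BID if symptoms have resolved or fallen to grade 1. If they persist or recur at grade 2 or higher, treatment stops for 4 weeks and the original ramp is repeated.
- **Section 5.5, general rules.** Grade 1 and 2 toxicities need no dose modification, and re-escalation is not allowed in this study.

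No passage sets an order of precedence.

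**The concern.** Section 5.5.1 names gastrointestinal effects as the major toxicity limiting metformin dose. Cycles 1 and 2 are the only period in which arm B takes metformin without bicalutamide. If one event can lead a site to wait and step up, to thin out the intakes, to cut and resume, or to stop for 4 weeks, two consequences follow. Patients with the same toxicity are handled differently. Metformin exposure also varies at two points that matter: the start of bicalutamide, and the week-9 fasting glucose and insulin samples. Section 8.3 makes those samples mandatory and plans to use the change in insulin over 9 weeks as a predictor.

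**Working it through.** **Can the instructions be followed together? By position in the ramp:**

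- *Week 1, Dose Level -2.* The table's reduction is to 500 mg BID, the dose already being taken.
- *Week 2, Dose Level -1.* Section 5.3.2 waits for resolution and then moves up one level. The table moves down one level for a week and then goes straight to 1000 mg BID, bypassing 1500 mg/day. The text prescribes a third pattern.
- *Weeks 3-4, Dose Level 0.* The patient is at full dose but still within the 4-week window of 5.3.2. That section directs a step to a level that does not exist, while the table directs a reduction. This is the clearest collision.
- *Section 5.5.* For grade 2 it conflicts with the table's reduction. Its bar on re-escalation conflicts with the table's return to full dose.

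**How far can exposure differ?** The plan states no exposure figure, so there is none to reproduce. I summed days × g/day over the lead-in for one hypothetical patient.

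Inputs:

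- Lead-in is cycles 1 and 2, with "One cycle = 28 days = 4 weeks" (section 5.3): 2 × 28 = 56 days. Section 9.2.8 labels the start of cycle 3 as week 13, which does not fit this; I use the cycle definition.
- Scheduled doses are those of 5.3.2: "The target dose of metformin is 1000 mg BID".

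Assumptions:

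- Section 5.3.2 means holding the current dose until the 2-week review, with toxicity resolved by then.
- The 5.5.1 text starts at once, at 0.5 to 1.0 g per intake.
- Under the table, toxicity either resolves within a week or persists beyond it.

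Planned total: 7×1.0 + 7×1.5 + 42×2.0 = 7 + 10.5 + 84 = **101.5 g**.

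Onset at the end of week 2 (17.5 g taken, 42 days left):

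- 5.3.2: 17.5 + 14×1.5 + 28×2.0 = 17.5 + 21 + 56 = **94.5 g**
- Text, 0.5 g per intake: 17.5 + 7×0.5 + 14×0.5 + 14×1.0 = 17.5 + 3.5 + 7 + 14 = **42 g**
- Text, 1.0 g per intake: 17.5 + 7×1.0 + 14×1.0 + 14×2.0 = 17.5 + 7 + 14 + 28 = **66.5 g**
- Table, resolved in a week: 17.5 + 7×1.0 + 35×2.0 = 17.5 + 7 + 70 = **94.5 g**
- Table, persistent: 17.5 + 7×1.0 + 28×0 + 7×1.0 = **31.5 g**

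The 5.3.2-to-table ratio is 94.5/94.5 = 1.0 or 94.5/31.5 = 3.0.

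Other onsets:

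- Day 8 (7 g taken). 5.3.2: 7 + 14×1.0 + 7×1.5 + 28×2.0 = 87.5. Table, resolved: 7 + 7×1.0 + 42×2.0 = 98. Table, persistent: 7 + 7×1.0 + 28×0 + 7×1.0 + 7×1.5 = 31.5.
- Day 22 (31.5 g taken). 5.3.2: 31.5 + 35×2.0 = 101.5. Table, resolved: 31.5 + 7×1.0 + 28×2.0 = 94.5. Table, persistent: 31.5 + 7×1.0 + 28×0 = 38.5.

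| Onset | 5.3.2 (g) | Table, resolved (g) | Table, persistent (g) | Ratio 5.3.2 / table |
|---|---|---|---|---|
| Day 8 | 87.5 | 98.0 | 31.5 | 0.89 or 2.78 |
| Day 15 | 94.5 | 94.5 | 31.5 | 1.00 or 3.00 |
| Day 22 | 101.5 | 94.5 | 38.5 | 1.07 or 2.64 |

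For day-15 onset lasting beyond a week, the dose on the first day of cycle 3 is 2.0 g/day under 5.3.2, 1.5 g/day under the table (second week of the repeated ramp), and 1.0 or 2.0 g/day under the text.

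**The case against.** The best defence is that the passages have different jobs. Section 5.3.2 can be read as a gate on escalation, with 5.5.1 governing the dose meanwhile; it does not say what is taken while waiting, so holding the dose is my assumption. The table speaks of reducing to 500 mg BID and resuming full dose, which suits a patient already at 1000 mg BID. Its grade 1 row does send patients with symptoms in the ramp-up to the grade 2 instructions, but in context that may mean a repeat ramp after full dose. The general sentence in 5.5 on grades 1-2 may yield to the specific table.

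These readings narrow the conflict but do not remove it. The table has no stated scope limit, and weeks 3-4 fall under both it and 5.3.2 on any reading. As a gate, 5.3.2 still releases the next step after a 2-weekly review, whereas the table resumes full dose after one week. The bar on re-escalation carries no exception.

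Two objections to size stand in full. Threefold is the extreme of the courses examined: it needs day-15 onset and toxicity that outlasts one week but resolves by two. With resolution inside a week, 5.3.2 and the table give the same total. A reader might also infer from section 1.3 that more than 1 in 10 patients would be affected; that figure carries no grade, and the same passage calls these effects usually transient.

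**Conclusion.** The inconsistency is real and should be corrected. The rules cannot all be followed for the same event, most clearly in weeks 3-4.

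The 5.3.2-to-table exposure ratio runs from about 1 to about 3, depending on onset and course. The text adds a further 42 to 66.5 g range for day-15 onset because its dose per intake is unstated. These totals rest on the assumptions listed above; the protocol gives no exposure figures.

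A reader might infer that a threefold difference is typical, or that the primary comparison is compromised. The documents support neither. They give no rate for grade 2 or higher events, so the number affected among the nominal 44 arm B patients is unknown. The primary endpoint is at week 32, which is 24 weeks after the lead-in ends, and no effect on it is shown. Sample size, type I error and power are untouched. The harm is inconsistent site handling and variable metformin exposure at the start of bicalutamide and at the week-9 research bloods.

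**What to change.** The sponsor should reconcile the Schema and sections 5.3.2, 5.5 and 5.5.1 into one algorithm for gastrointestinal toxicity early in metformin treatment, stated once and cross-referenced elsewhere. It should:

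- give the dose per intake at every step;
- say what applies at Dose Level -2 and at Dose Level 0;
- state its precedence over the general rules in 5.5, including the bar on re-escalation.

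Any 2-weekly evaluation that is kept should be reconciled with Table 1 in section 6.1, which schedules assessments by 4-week cycle. The pointer in 9.1.8 to section 5.4.3 for dose escalation should be corrected too, since 5.4.3 contains none. Which rule is right is the sponsor's clinical decision.

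The cost is a wording amendment and a site memo. Extra visits arise only if 2-weekly evaluations are retained and added to the schedule.

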5.4 Guideline for Study Medication Administration

5.4.1 Pill Diary

A blank pill diary (Appendix I) will be provided to the patient by the study coordinator at cycle 1 and at each subsequent visit, and a completed pill diary should be returned by the patient at Day 1 of cycle 2 and each subsequent cycle.

5.4.2 Bicalutamide

Bicalutamide will be self-administered by the patient once daily. It may be taken with or without food. The tablet should be taken at approximately the same time every day. Bicalutamide and metformin may be taken together.

5.4.3 Metformin

Metformin will be taken at the assigned dose twice daily. Metformin is administered orally, with food. Bicalutamide and metformin may be taken together.

5.4.4 Missed doses

Patients who forget to take their scheduled dose of study drug should be instructed not to make up the missed dose. Missed doses of study drug should be recorded in the patient's study record.

5.5 Dose Modifications

All toxicities should be graded according to the Version 4.0 of the NCI Common Terminology Criteria for Adverse Events (CTCAE). Dose modifications will be based on the highest grade since the prior dose and will be performed as outlined below depending on the type and severity of the toxicity encountered, provided that the criteria have not been met for subject withdrawal from study. Patients will be withdrawn from the study if they fail to recover to CTCAE grade 0-2 (or within 1 grade of starting values of pre-existing laboratory abnormalities) from a treatment related toxicity within 4 weeks. Treatment may be delayed no more than 4 consecutive weeks to allow recovery from toxicity or the patient will be removed from the study. Dose modifications are not necessary for Grade 1 or 2 toxicities. The reason for dose modification, delay, and missed doses must be detailed in the source document. Dose re-escalation will not be allowed during this study.

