Hepatic dysfunction* AST or ALT=1.8- 3.0 X ULN		Repeat AST & ALT in 2 weeks. If either AST or ALT > 1.8 X ULN, continue at discretion of Investigator, monitoring AST & ALT every two weeks until both < 1.8 X ULN – then resume annual testing. If Investigator decides to stop medication, resume once AST & ALT < 1.8 X ULN, starting with 500 mg BID for 4 weeks, then increasing to 2 tablets per day with annual AST & ALT assessments
Hepatic dysfunction* AST or ALT > 3.0 X ULN		Hold study drug. Repeat LFTs in 2 weeks. If AST and ALT < 1.8 ULN, resume medication. Resumption involves 500 mg BID for 4 weeks, then increase to 1000mg BID per day with resumption of protocol specified monitoring if both AST and ALT remain at < 1.8 x ULN. If repeat AST and ALT are 1.8-3.0 x ULN, follow steps as described in section above. If AST and/or ALT > 3.0 x ULN, initiate workup for liver disease. If AST or ALT=1.8-3.0 resume medication at the discretion of the investigator.
Renal dysfunction Creatinine > 115 µmol/L 1.3 mg/dL		Hold study drug for up to 4 weeks. After resolution of event, use ramp-up schedule.
Clinical diagnosis of congestive heart failure	> Grade 3	Hold study drug for up to 4 weeks. Re-start may be considered if underlying condition (e.g. acute MI) has resolved. If Metformin is started after CHF, the ramp-up schedule should be used. Do not re-start if symptoms persist or ongoing treatment of CHF is required.
Acidosis (Lactate > 5.0 mM) (pH < 7.3)	Grade 3	Stop study drug and do not re-start. Report as a serious adverse event.
Anemia Hgb < 110 or MCV > 105	> Grade 1	Perform CBC and serum B12 level. Initiate anemia workup if cause of anemia not apparent. Continue at full dose. (Treatment is not held for anemia regardless of toxicity grade.)
Skin Reactions Major – generalized urticaria, bullous rashes, exfoliative dermatitis	Generalized	Stop study drug and do not re-start

Stevens Johnson Syndrome Localized	Localized	Hold study drug for up to 4 weeks if possibly, probably or definitely related to study drug. When rash clears, 500 mg BID per day for 4 weeks, then 1000 mg BID per day – if rash recurs, and is thought to be possibly, probably or definitely related to study medication, discontinue study medication.

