5.5.2. Dose Modifications for Bicalutamide

Not allowed. In case of CTCAE grade 3 or 4 transaminase elevation, bicalutamide will be stopped until the event resolved to Grade 1 or less.

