5.6 Duration of Therapy

In the absence of treatment delays due to adverse events, treatment may continue for 8 cycles (32 weeks) or until one of the following criteria applies:

- Disease progression
- Intercurrent illness that prevents further administration of treatment,
- Unacceptable adverse event(s)
- Patient decides to withdraw from the study
- General or specific changes in the patient's condition render the patient unacceptable for further treatment in the judgment of the investigator.

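### The 4-week exit rules in section 5.5 are not limited to the drug that caused the toxicity, so metformin toxicity can cost an arm B man his bicalutamide and perhaps his week-32 PSA

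*Combined protocol and SAP*

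**What the plan says.** Section 5.5 applies to both drugs and comes before the drug-specific sections. It has two exit rules. On unresolved treatment-related toxicity: "Patients will be withdrawn from the study if they fail to recover to CTCAE grade 0-2", with a 4-week limit and an allowance for pre-existing laboratory abnormalities. On delay: "Treatment may be delayed no more than 4 consecutive weeks to allow recovery from toxicity or the patient will be removed from the study". Neither names a drug. The same paragraph makes dose modification conditional on the withdrawal criteria not having been met, so the exit rules outrank the tables that follow.

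Section 5.5.1 (metformin) works differently. On gastrointestinal intolerance: "Subjects not tolerating study medication after this approach may go off study treatment but Investigators are urged to re-challenge willing subjects 4 weeks later". The gastrointestinal row of its table ends with the instruction that "the maximum tolerated dose should be used for the remainder of the study". The renal row reads "Hold study drug for up to 4 weeks. After resolution of event, use ramp-up schedule". The heart-failure row names the drug: "If Metformin is started after CHF, the ramp-up schedule should be used". Acidosis and generalised skin reactions stop the drug for good.

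Section 5.5.2 (bicalutamide) begins "Not allowed. In case of CTCAE grade 3 or 4 transaminase elevation", which leads to a hold until grade 1 or less. It does not mention metformin. Section 5.6 lists unacceptable adverse events among the reasons to end treatment, again without naming a drug.

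Under 5.3.1 and 5.3.2, arm A is observed untreated in cycles 1-2 while arm B takes metformin alone. Both arms take bicalutamide in cycles 3-8.

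**The concern.** The trial asks what metformin adds to bicalutamide, so bicalutamide should be the same in both arms. The primary endpoint, undetectable PSA at week 32, can be expected to depend largely on it. If an exit for metformin toxicity also ends bicalutamide, arm B loses the shared drug for a reason that cannot arise in arm A. The comparison then mixes the effect of adding metformin with the effect of some arm B men going without bicalutamide.

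The endpoint measurement is also at risk. Section 5.9 follows all patients for response over 32 weeks, and footnote 7 to Table 1 puts the off-treatment evaluation at week 33. Section 6.4 puts that evaluation at the point when a man comes off treatment or completes it. For a man removed in week 8 these give different answers, and 5.5 says that he has left the study. Two sites could handle the same man differently.

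**Working it through.** **1. Is there a rule that protects bicalutamide?** I looked for one in each place where it might stand.
- 5.5: exit is from the study; no drug is named.
- 5.5.1: describes how to hold, restart or stop metformin; silent on bicalutamide.
- 5.5.2: covers only bicalutamide's own transaminase hold.
- 5.3.2: starts bicalutamide in cycle 3, but in a man continuing metformin at his maximum tolerated dose.
- 5.9: follow-up for response; says nothing about continuing a drug.

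None states that bicalutamide starts or continues once metformin has stopped for good.

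**2. Timing.** Cycle 3 day 1 is day 2 × 28 + 1 = 57. A metformin hold that begins before day 29 and is still running on day 57 has lasted more than 28 days. The delay rule, read literally, then removes the man before or on the day bicalutamide is due. In arm A there is no drug to hold in that period.

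**3. Reproducing the design.** Section 11.1 gives 26 and 13 men in the first cohort (arms B and A), and 44 and 22 in total. Continue if 13·E1 − 26·C1 > −52 and E1 ≥ 6. Reject if 22(E1+E2) − 44(C1+C2) ≥ 88 and E1+E2 ≥ 14. Exact enumeration of the four independent binomials gives:
- 20% v 20%: type I error 3.25% (plan: 3.24%), early stop 60.05% (plan: 60%).
- 20% v 40%: power 80.36% (plan: 80.3%), early stop 3.24% (plan: 3.23%).

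**4. If affected men count as failures.** Let d be the share of arm B that stops metformin for good. The documents give no value; those below are assumptions. Stoppers who keep bicalutamide are assumed to respond at 20%, the arm A rate. There are two readings of the planned 40%:
- Reading A, 40% only in men who stay on metformin. Bicalutamide lost: 0.40(1 − d). Kept: 0.40(1 − d) + 0.20d.
- Reading B, 40% is the whole-arm rate with stoppers kept on bicalutamide. Lost: 0.40 − 0.20d. Kept: 0.40.

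| d | A: lost v kept | A: loss | B: lost v kept | B: loss |
|---|---|---|---|---|
| 1/44 | 77.5% v 79.0% | 1.5 points | 79.0% v 80.4% | 1.4 points |
| 5% (about 2 men) | 73.7% v 77.2% | 3.5 points | 77.2% v 80.4% | 3.2 points |
| 10% (about 4 men) | 65.6% v 73.7% | 8.1 points | 73.7% v 80.4% | 6.7 points |

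Example, d = 5%, Reading A: lost 0.40 × 0.95 = 0.38; kept 0.38 + 0.20 × 0.05 = 0.39.

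If half of the affected men stop late enough to respond at 20% anyway, the loss is about 1.5 to 1.7 points at 5% and 3.2 to 3.9 at 10%. At a common 20% rate, with affected men scored as failures (arm B rate 0.20(1 − d)), the chance of rejecting falls from 3.2% to 2.2% at 5% and 1.4% at 10%.

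**5. If they are excluded.** Section 11.4 defines treated arm B subjects by receipt of both drugs, so a man removed before bicalutamide falls outside that set. With the same cut-offs (88 and 14) and 40% in those who remain, dropping 2 men gives power 74.7% and dropping 4 gives 70.8%. The larger problem is that removal then depends on post-randomisation toxicity that arises in one arm only. The remaining groups are no longer those created by randomisation, and the direction of any bias cannot be known in advance.

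**The case against.** The best defence is that the documents as a whole point to single-drug stopping. The 5.5.1 rows are written for metformin. A man who can be re-challenged is evidently still on study. Section 9.1.12, which ends study treatment on a new diabetes diagnosis, sits in the metformin section and reads most naturally as stopping metformin. Section 11.5 provides for describing discontinuation of any study drug. Sensible investigators might well keep such men on bicalutamide. This stands as evidence of what was foreseen. It does not replace a rule, because 5.5 places its exits above the tables.

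A reader might infer that any 4-week metformin hold costs a man his bicalutamide, for instance one begun at cycle 2 day 1 for raised creatinine. The documents do not support that. From day 29 to day 57 is exactly 4 weeks, which the delay rule allows, and bicalutamide is due that same day. The recovery rule applies only to toxicity still above grade 2, apart from its allowance for pre-existing abnormalities. The hold must start earlier or run longer.

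The footnote 7 and 6.4 wording can also be reconciled, with week 33 for completers and an earlier visit for others. That leaves a gap for early stoppers and not a flat contradiction.

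Finally, in cycles 3-8 liver toxicity may come from either drug, so an exit covering both is sometimes right. The fix allows for this.

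**Conclusion.** The point holds as a gap in a stated rule: 5.5 does not confine its exits to the drug responsible, and no text secures bicalutamide or the endpoint PSA for a man who stops metformin. It does not show that the plan intends such men to lose bicalutamide, or that many would.

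The number is probably small. Gastrointestinal intolerance, which 5.5.1 treats as the main dose-limiting toxicity, leads to the maximum tolerated dose and not to exit. Section 11.2 expects a DLT rate of 5% in arm B; that is a reference point and not a rate of permanent stopping. Still, the exact power of 80.4% leaves almost no margin over the 80% claimed in 11.1, so one affected man scored as a failure brings it below that level.

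The power figures rest on three assumptions: the stopping rate, failure scoring, and a 20% response in stoppers who keep bicalutamide. A reader might infer a raised false-positive risk. Under failure scoring the opposite holds. Under exclusion the documents do not allow the size or direction of bias to be stated.

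**What to change.** Amend the wording:
1. In 5.5, apply both 4-week exit rules to the drug being held, and state that permanently stopping metformin is not removal from the study.
2. State that bicalutamide then starts at cycle 3 day 1 or continues, unless 5.5.2, toxicity possibly due to bicalutamide, or another safety reason applies. Where attribution is unclear, both drugs may be stopped.
3. In every case take the week 32/33 PSA and count the man in the arm to which he was randomised.
4. Align 6.4 and 11.4 with this.

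No extra patients are needed. The cost is that early stoppers keep the scheduled visits, and that arm B will include some men on bicalutamide alone. The result then describes the assigned strategy and not metformin as actually taken, which is the usual reading of a randomised comparison.

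### Section 5.5's Grade 1–2 sentence and its ban on re-escalation do not agree with the metformin tables in 5.5.1, and no text says which governs

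*Combined protocol and SAP*

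**What the plan says.** Section 5.5 (Dose Modifications) sets the general rules for both drugs in one paragraph. It says that modifications "will be performed as outlined below depending on the type and severity of the toxicity encountered". Later in that paragraph it says that "Dose modifications are not necessary for Grade 1 or 2 toxicities", with no exception by drug or event. It closes by disallowing re-escalation for the whole study.

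Section 5.5.1 (Dose Modifications for Metformin) says "Dose adjustments, for reasons of toxicity, will be as in the tables below". Three parts of those tables matter here:

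- **Gastrointestinal toxicity, Grade 2 or higher:** "Reduce to 500 mg BID for one week", then back to full dose if symptoms have gone or are Grade 1 only. "If symptoms persist or recur at Grade 2 or higher, stop study treatment for 4 weeks", followed by a restart on the original ramp-up and, where needed, a second attempt at full dose.
- **Bilirubin above ULN, Grade 1 or greater, Gilbert's disease excepted:** "Hold study drug for up to 4 weeks. If bilirubin returns to normal within that time frame, begin 500 mg BID for 4 weeks", and after that 1000 mg BID.
- **Gastrointestinal toxicity, Grade 1:** the man is encouraged to stay on full dose, and drug is interrupted for a week only if he is unwilling.

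Section 5.3.2 (repeated in the Schema) makes each ramp-up step conditional on there being no gastrointestinal toxicity of Grade 2 or above. Section 5.5.2 has bicalutamide stopped only for Grade 3 or 4 transaminase elevation.

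**The concern.** The protocol has two sets of instructions for the same event. On the plain words of 5.5, a man with Grade 2 diarrhoea or a Grade 1 bilirubin rise needs no change of dose. On the words of 5.5.1, the first man's dose is reduced and the second man's drug is held. If a site then follows the table and takes him back to full dose, it breaks the re-escalation sentence in 5.5.

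This bears first on patient management and safety. It also bears on the analysis. Safety and tolerability of metformin is a secondary objective (section 2.2), and only arm B takes metformin. Dose received, interruptions and the count of protocol deviations in that arm could therefore depend on which sentence a site applied. Section 5.5.1 itself names gastrointestinal effects as the main dose-limiting toxicity, so the affected rows are not peripheral.

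**Working it through.** The plan gives no figure to reproduce. The check is a comparison of the texts, followed by arithmetic on dose received.

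**Step 1: set the rules side by side.**

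| Event | Section 5.5 | Tables in 5.5.1 | Compatible? |
|---|---|---|---|
| Gastrointestinal, Grade 1 | No change needed | Full dose encouraged; one-week stop only if the man is unwilling | Largely yes |
| Gastrointestinal, Grade 2 | No change needed | Reduce for one week; four-week stop if it persists or recurs | No |
| Gastrointestinal, Grade 3 or higher | Outside the Grade 1–2 sentence | Same row as Grade 2 | Yes, on that sentence |
| Bilirubin above ULN, Grade 1 or 2 | No change needed | Hold up to four weeks, then half dose for four weeks | No |
| Return to full dose after a reduction | Not allowed | Directed | No |

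The rows for transaminases, creatinine and localized skin reactions are triggered by laboratory values or extent, not by a stated grade. They are therefore not counted against the Grade 1–2 sentence, but where they reduce the dose and then raise it again they do meet the re-escalation ban. The bicalutamide rule acts only at Grade 3 or 4, so it fits 5.5. The conflict is confined to metformin.

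**Step 2: look for a rule of precedence.** Section 5.5 refers forward to what is outlined below, and 5.5.1 refers to its tables. Both point toward the tables. The Grade 1–2 sentence comes after that pointer in the same paragraph and carries no exception. Neither section says that the tables override it or the re-escalation ban.

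**Step 3: size of the difference for one man.** Inputs: full dose 1000 mg BID = 2000 mg/day; 500 mg BID = 1000 mg/day, or 0.5 of full; ramp-up week 2 = 1500 mg/day, or 0.75 of full; treatment lasts 32 weeks (5.3.2, 5.6). Loss is counted in full-dose weeks against staying at full dose.

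- Gastrointestinal Grade 2, resolved after one week: 1 × 0.5 = 0.5 weeks; 0.5/32 = 1.6%.
- Gastrointestinal Grade 2, persisting, then tolerating the restart: 0.5 (half dose) + 4 (stop) + 0.5 (ramp week 1) + 0.25 (ramp week 2) = 5.25 weeks; 5.25/32 = 16%.
- Bilirubin, longest hold: 4 × 1 + 4 × 0.5 = 6 weeks; 6/32 = 19%.
- Reduction to 500 mg BID with the re-escalation ban applied literally. The timing is an assumption. Reduced from the start of week 4 (full dose is reached in week 3): 29 × 0.5 = 14.5 weeks; 14.5/32 = 45%. Reduced from the start of cycle 8 (week 29): 4 × 0.5 = 2 weeks; 2/32 = 6%. Under the table, the same man loses 0.5 weeks if symptoms settle in a week.

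Counting the planned ramp-up at its true dose changes the denominator to 0.5 + 0.75 + 30 = 31.25 weeks, which alters these percentages by about one point or less.

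**Step 4: number of men.** Section 1.3 puts gastrointestinal effects of metformin above 1 in 10 and hepatic dysfunction below 1 in 10,000. Neither figure is split by grade, so the number who would meet the conflict cannot be derived.

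**The case against.** The best reply is that 5.5, read in full, already sends the site to the tables. The pointer ties modifications to the type and severity of the toxicity, the tables are directive, and saying that a change is not necessary does not forbid one. A careful site would probably follow the specific rule. This stands in part: the texts are in conflict, but they are not flatly opposite orders, and a reader who concludes that sites will keep full dose through these events goes further than the documents do. Nothing in them shows how sites read the paragraph. What remains is that the precedence has to be inferred. The inference also does not resolve the re-escalation ban, which is a prohibition against a direct instruction and does not depend on any permissive wording.

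A reader might also infer that the conflict covers the commonest events generally, or that at least four or five of arm B's nominal 44 men would meet it (44 × 0.1 = 4.4). The documents do not support either inference. Only gastrointestinal toxicity is described as common. The 1-in-10 rate covers all grades, while the conflict sits at Grade 2, since Grade 1 handling largely agrees and Grade 3 is outside the sentence. The 44 applies only if the second cohort opens; the first has nominally 26 men in arm B.

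The rarity of metformin hepatic dysfunction does not empty the bilirubin row. The row is not restricted to metformin causation, bilirubin must be normal at entry (3.1.14), chemistries are drawn every four weeks (6.3), and arm B men also take bicalutamide, for which 9.2.10 cites severe liver injury in about 1%.

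The ramp-up rule in 5.3.2 is weaker evidence. It withholds a planned increase and orders no reduction, so it is a text to check for consistency and not a further contradiction of the Grade 1–2 sentence.

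**Conclusion.** The concern holds in a limited form. Two general statements in 5.5 disagree with the metformin tables in 5.5.1: one on Grade 2 gastrointestinal toxicity and Grade 1–2 bilirubin rises, the other on going back to full dose after any reduction. This is an error in the current text, not a missing detail. It affects arm B only.

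For an individual, the choice of text is worth between 0.5 and 6 full-dose weeks out of 32 for a single episode handled under the tables by the branches worked above. The upper figures describe the persistent or longest-hold branch, not the typical man. If the re-escalation ban is applied after a reduction, the loss could reach 14.5 weeks under the assumed earliest timing. The number of men affected is unknown.

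No effect on the 32-week PSA comparison or on the toxicity stopping rule in 11.2 has been shown, and none is claimed. The point should be corrected because it concerns patient management and the correction is cheap.

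**What to change.** The sponsor should reconcile 5.5 with 5.5.1 and state in the text:

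1. which section governs Grade 1 and 2 metformin toxicities where the tables list the event;
2. whether the re-escalation ban applies to metformin, and if so how it fits with the table rows that return a man to full dose.

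Both sections should then be checked against the ramp-up rule in 5.3.2 and its copy in the Schema, so that a Grade 2 gastrointestinal event in the first four weeks has one instruction. Whether the general sentences are given a narrower scope or the tables are changed is a clinical decision for the sponsor; none is proposed here.

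The cost is a short amendment of a few sentences. Sample size, visits and the planned analyses are untouched. Correcting the Grade 1–2 sentence alone would leave the re-escalation conflict in place, so both should be dealt with together.
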